#### **6.3.** Measures to Minimize Bias

Efforts will be made to ensure a representative sample of the local FM community participates in the study. The chance of observer bias is minimized by the use of widely used, validated objective measures during the study. However, as this is an open-label pilot study, sources of bias will remain.

# **6.4.** Study Intervention Compliance

Participants will receive study intervention directly from the Investigator or designee, under medical supervision. The date and time of each dose administered in the clinic will be recorded in the source documents. The dose of study intervention and study participant identification will be confirmed at the time of dosing by a member of the study site staff other than the person administering the study intervention. Study site staff will examine each participant's mouth to ensure that the study intervention was ingested.

#### 6.5. Dose Modification

The only dose modification allowed would be with the second dose (of 2 planned doses) to be 15 mg (instead of 25 mg) if the participant or Investigator determines that the higher dose is not advantageous and may not provide further benefit.

CONFIDENTIAL 36 27 February, 2024

The reason for dose modification must be noted in the source documents and case report form (CRF).

Note: If participants exhibit an increased risk of harm to self or others, or any other sign that continuing in the study would present undue risks the second dose should not be administered. Similarly, participants will not be allowed to continue with a second dose if they have adverse events such as psychosis or hypertension.

# 6.6. Continued Access to Study Intervention after the End of the Study

There are no provisions for any participant for extending the study or for entry to roll-over studies. There is no intervention planned after the end of the study.

## 6.7. Treatment of Overdose

For this study, any dose of TRP-8802 greater than the intended dose (15 mg [Day 22] or 25 mg [Day 36]) in a 24-hour time period will be considered an overdose.

No confirmed incidences of an overdose of pharmaceutical psilocybin have been reported. Previous clinical trials involved single or multiple doses of oral psilocybin in predefined quantities administered in a controlled environment. Should an accidental overdose occur, appropriate symptomatic measures should be initiated, followed by monitoring any AEs to resolution.

In the event of an overdose, the site staff should immediately contact the site physician, who will determine whether the participant should be treated with rescue medication and if further treatment is needed (e.g., emergency department visit). The participant should be closely monitored for any AE/SAE for at least 1 day. The quantity of the excess dose(s) should be documented in the source documents and the Study Drug Administration CRF.

# **6.8.** Concomitant Therapy

Any medication or vaccine (including over the counter or prescription medicines, recreational drugs, vitamins, and/or herbal supplements) that the participant receives beginning at the time of screening or receives during the study must be recorded along with:

- reason for use
- dates of administration including start and end dates
- dosage information including dose and frequency

The Sponsor should be contacted if there are any questions regarding concomitant or prior therapy.

Participants must abstain from taking nonprescription drugs (including vitamins, recreational drugs, and dietary or herbal supplements) within 7 days before each study drug session day, unless, in the opinion of the investigator and sponsor, the medication will not interfere with the study.

CONFIDENTIAL 37 27 February, 2024

## **6.8.1.** Rescue Medicine

The session therapists are trained to reassure the participants if they experience acute anxiety, agitation, paranoia, or panic. However, in the unlikely event that those symptoms do not respond to reassurance, or if a participant experiences a severe AE outside of the expected challenging experiences associated with psilocybin therapy, one of the session therapists will contact the on-call study physician. The study physician will use their clinical judgment to determine the most appropriate medical intervention.

The study site will supply rescue medication that will be obtained locally. The following rescue medications may be used:

- In the event of a psychiatric emergency, an oral benzodiazepine (e.g., lorazepam) will be available for on-site treatment of panic or anxiety. An oral antipsychotic (e.g., risperidone) will be available for on-site treatment of psychosis or severe agitation.
- In the event of symptomatic hypertension, labetalol or similar will be available for on-site treatment of symptomatic hypertension.
- In the event of new-onset chest pain, the participant will be evaluated in-person by the study physician to determine whether the pain is cardiovascular, musculoskeletal, or reflects acute panic/anxiety. Vital signs and ECG will be monitored (and compared to baseline measurements) for evidence of acute ischemia. Based on physician judgment, sublingual nitroglycerin (available on-site) may be administered as the standard of care for cardiac chest pain while Emergency Medical Services is called to transport the participant to an emergency department. The goal will be to transport an acutely decompensating patient to an emergency department prior to the point where advanced cardiac life support care is required.
- In the event of headache, ibuprofen (400 mg orally) or similar will be available for onsite treatment. If the study physician decides that the use of a rescue medication is warranted, then the study physician or a member of the nursing staff will administer the medication to the participant.

The date and time of rescue medication administration as well as the name and dosage regimen of the rescue medication must be recorded in the CRF. In the unlikely event that a medical or psychiatric emergency occurs during a drug session and cannot be safely managed by study personnel using reassurance or medication, study staff will contact 911 so that the participant can be transported to an emergency medical department.

In the event that rescue medication is needed, the Investigator and study physicians may use their clinical judgment to implement a future dose modification (Section 6.5) or to discontinue future study intervention (Section 7.1) for that participant.

CONFIDENTIAL 38 27 February, 2024

## 7.1.1. Temporary Discontinuation

Temporary discontinuation of study intervention will not be allowed. A participant who discontinues study intervention will be considered to be discontinued from the study.

# 7.2. Participant Discontinuation/Withdrawal from the Study

- A participant may withdraw from the study at any time at his/her own request or may be withdrawn at any time at the discretion of the investigator for safety, behavioral, or compliance reasons. This is expected to be uncommon.
- At the time of discontinuing from the study, if possible, the EOT and follow-up visits should be conducted, as shown in the SoA (Section 1.3). See SoA for data to be collected at the time of study discontinuation and follow-up.
- If the participant withdraws consent for disclosure of future information, the sponsor may retain and continue to use any data collected before such a withdrawal of consent.

# 7.3. Lost to Follow up

A participant will be considered lost to follow-up if he or she repeatedly fails to return for scheduled visits and is unable to be contacted by the study site.

The following actions must be taken if a participant fails to return to the clinic for a required study visit:

• The site must attempt to contact the participant and reschedule the missed visit as soon as possible and counsel the participant on the importance of maintaining the assigned visit schedule and ascertain whether or not the participant wishes to and/or should continue in the study.

CONFIDENTIAL 39 27 February, 2024

• Before a participant is deemed lost to follow up, the investigator or designee must make every effort to regain contact with the participant (where possible, 3 telephone calls and, if necessary, a certified letter to the participant's last known mailing address or local equivalent methods). These contact attempts should be documented in the participant's research record.

- Should the participant continue to be unreachable, he/she will be considered to have withdrawn from the study.
- Site personnel will attempt to collect the vital status of the participant within legal and ethical boundaries for all participants enrolled, including those who did not get study intervention. Public sources may be searched for vital status information. If vital status is determined as deceased, this will be documented and the participant will not be considered lost to follow-up. Sponsor personnel will not be involved in any attempts to collect vital status information.

Discontinuation of a specific site or of the study as a whole is presented in Appendix 1 (Section 10.1.9).

CONFIDENTIAL 40 27 February, 2024

# 8. Study Assessments and Procedures

• Study procedures and their timing are summarized in the SoA (Section 1.3). Protocol waivers or exemptions are not allowed.

- Immediate safety concerns should be discussed with the sponsor immediately upon occurrence or awareness to determine if the participant should continue or discontinue study intervention.
- Adherence to the study design requirements, including those specified in the SoA, is essential and required for study conduct.
- All screening evaluations must be completed and reviewed to confirm that potential
  participants meet all eligibility criteria. The investigator will maintain a screening log to
  record details of all participants screened and to confirm eligibility or record reasons for
  screening failure, as applicable.
- Audio and video recordings will be made for the length of the dosing session days. The recordings will be used for quality assurance and staff training purposes; they will not be used for any other purpose for this study.

# 8.1. Safety Assessments (Primary Endpoints)

Planned time points for all safety assessments are provided in the SoA (Section 1.3). Safety assessments will always be performed before efficacy assessments at each visit.

## 8.1.1. Vital Signs

Heart rate and BP will be assessed before TRP-8802 capsule administration and at 30, 60, 90, 120, 180, 240, 300, and 360 minutes after capsule administration. Blood pressure and pulse measurements should be preceded by at least 5 minutes of rest for the participant in a quiet setting without distractions (e.g., television, cell phones). Blood pressure and pulse measurements will be assessed with a completely automated device. Manual techniques will be used only if an automated device is not available. If a patient's blood pressure is >200 systolic or >110 diastolic for more than 15 minutes (i.e. 4 consecutive readings) they will be transferred to ED whether or not they are symptomatic.

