Higher doses of psilocybin (greater than 0.3 mg/kg) also may transiently lead to elevated mean BP, peaking 30 to 60 minutes following psilocybin administration and returning to baseline levels after 90 to 180 minutes without necessitating further interventions (Griffiths 2006; Hasler 2004). The severity of elevations in BP was usually asymptomatic and was graded as mild or moderate. Although several subjects in a University of Wisconsin dose-escalation study reached BP elevations that were graded as moderate, they remained asymptomatic (Brown 2017). It is not clear whether the changes in BP and HR are due to the elevated psilocin concentration directly or to the psychedelic effect caused by this active metabolite. Psilocybin appears to produce only slight sympathetic system activation (Hasler 2004; Gouzoulis-Mayfrank 1999).

Transient elevations of HR were common in subjects receiving psilocybin at doses of 0.3 mg/kg or more. The time course of these elevations in HR is similar to those seen for the elevation in BP, peaking between 60 to 120 minutes after the dose. This is similar to time of peak psilocin concentrations and peak psychedelic effect. Again, it is not clear whether or not the changes in BP and HR are directly due to the elevated psilocin concentration or caused indirectly by the psychedelic effect. In a phase 1 dose-escalation study in healthy volunteers, there were several instances in which mild bradycardia and tachycardia were noted. Psilocybin resulted in an increased HR, with slightly higher mean change from baseline in HR ( $\Delta$ HR) at higher psilocybin doses and corresponding higher psilocin exposures (Dahmane 2021). The maximum mean  $\Delta$ HR was observed at the time of psilocin maximum observed concentration (Cmax) (i.e., at 2 hours post dose) in nearly all psilocybin dose groups, and mean  $\Delta$ HR decreased with decreasing psilocin concentration at subsequent time points. Instances of bradycardia or tachycardia were unimodal, with no swing between bradycardia and tachycardia after a given dose. The episodes of bradycardia and tachycardia reported in recent studies were asymptomatic ("mild" or Grade 1) and did not require treatment (Tryp-8802 IB). Further information can be found in the current Tryp-8802 IB.

Mild headaches are common within the 24 hours after a dose of psilocybin. No auras or photo/phonophobia are associated with these headaches, which respond well to a single dose of

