During the dosing sessions, which will take at least 8 hours, two therapists will be present in the room and available to support participants' physical and emotional needs. A study physician will be on call and within 5 minutes of the session room during the first 3 hours or until the peak effects of psilocybin have abated, and will remain available for the remainder of the course of the TRP-8802 dosing session if needed for consultation. During these sessions, participants will be instructed to lie on a comfortable couch or bed, wear eyeshades, and listen to music through headphones, all of which are meant to enhance and encourage internal attention and reflection. Participants will be encouraged by the therapist to direct their attention inward. Recumbent BP and HR will be monitored (Section 8.1.1) until the drug effects have lessened. There will be an automated external defibrillator located on site and a crash cart containing medicine (Section 6.8.1) and equipment for emergency resuscitation.

During the same period as the vital signs measurements, therapists will also complete the monitor rating form, which includes questions about the presence/intensity of behaviors, signs, and reported symptoms, such as peacefulness, yawning, nausea/vomiting, quantity of speech, anxiety, sleepiness, crying, restlessness, visual changes, euphoria, and feelings of unreality. These sessions will be video and audio recorded. After the study drug effects have subsided, participants will complete questionnaires that assess the subjective experiences of the TRP-8802 dosing session, and the therapists will complete questionnaires that assess participant mood and safety. Participants will be asked to process the experience at home by writing a reflection about

CONFIDENTIAL 26 27 February, 2024

their experiences during the dosing session (Section 8.2.2.4). This reflection will be discussed at follow-up meetings.

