#### 6.1.2. Leaving the Research Unit

Participants will not be allowed to leave the research until the study staff makes the judgment that the effects of the study intervention have completely subsided. Participants will expected to be on the research site for at least 8 hours. The discharge criteria are as follows (all of the following must be met):

• A responsible friend/family member is available to accompany the participant home.

CONFIDENTIAL 35 27 February, 2024

• The participant's clinical status is not deemed to be of concern by the clinical judgment of a study physician.

- The participant is deemed by study staff to be free of any acute drug effects.
- The participant believes they have approximately returned to their psychological baseline.
- The study staff judges that it is safe to discharge the participant.
- The participant expresses a readiness to go home.

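### The ED-transfer rule for high blood pressure equates more than 15 minutes with four consecutive readings, but four scheduled readings span 90 to 180 minutes and no repeat interval is written

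*Combined protocol and SAP*

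**What the plan says.** **Transfer rule.** Sections 8.1.1 and 8.5 carry the same rule. A participant whose pressure is above 200 systolic or above 110 diastolic "for more than 15 minutes (i.e. 4 consecutive readings) they will be transferred to ED whether or not they are symptomatic".

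**Schedule.** Both sections set one reading before the capsule and then readings "at 30, 60, 90, 120, 180, 240, 300, and 360 minutes after capsule administration". Section 8.1.1 specifies an automated device and says that readings "should be preceded by at least 5 minutes of rest for the participant in a quiet setting".

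**Other monitoring text.** Section 4.1.4 says "Recumbent BP and HR will be monitored (Section 8.1.1) until the drug effects have lessened". It gives no interval and points back to 8.1.1. Nothing in the protocol orders a repeat after a high value or says how soon to take one.

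**Surrounding safeguards.** Section 4.1.4 keeps a study physician within 5 minutes of the room for the first 3 hours or until peak effects abate. Section 6.8.1 says that "labetalol or similar will be available for on-site treatment of symptomatic hypertension". Section 6.1.2 allows discharge only if the participant's "clinical status is not deemed to be of concern by the clinical judgment of a study physician".

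**Dose 2.** Section 6.5 says "participants will not be allowed to continue with a second dose if they have adverse events such as psychosis or hypertension". Section 7.1 repeats that sentence but limits it to serious adverse events.

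**The concern.** The parenthesis in the transfer rule makes the duration and the count one test. On the readings the protocol schedules, they are different tests. A team looking at a value over the limit is not told when to measure again, or which limb governs if the two disagree.

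This is the only numeric blood pressure limit for action written out in the protocol, and it covers participants without symptoms. The on-site antihypertensive is named for symptomatic hypertension, so for an asymptomatic participant this is the only written response specific to blood pressure. Vital signs during dosing are also part of the primary safety endpoint.

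Two careful teams could act differently on the same values. One might treat two successive high scheduled readings as more than 15 minutes and transfer. The other might wait for the fourth.

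**Working it through.** **Inputs.** Post-dose reading times from Section 8.1.1: 30, 60, 90, 120, 180, 240, 300 and 360 minutes. The gaps are 30 minutes up to the 120-minute reading and 60 minutes after it. The rule's own figure is that four consecutive readings correspond to more than 15 minutes.

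**Step 1: try to reproduce that figure on the written schedule.** The span of four consecutive readings is the time of the fourth minus the time of the first. The last column is the time of the fourth minus the time of the second, that is, how much later the count is met than a duration judged from two successive high readings.

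| First high reading (min) | Second | Fourth | Span of four | Fourth minus second |
|---|---|---|---|---|
| 30 | 60 | 120 | 90 | 60 |
| 60 | 90 | 180 | 120 | 90 |
| 90 | 120 | 240 | 150 | 120 |
| 120 | 180 | 300 | 180 | 120 |
| 180 | 240 | 360 | 180 | 120 |
| 240, 300 or 360 | – | not reached | – | – |

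The figure is not reproduced. The spans are 90 to 180 minutes, or 90/15 = 6 to 180/15 = 12 times the stated duration. Including the pre-dose reading does not help: 0 to 90 minutes is again a span of 90. From 240 minutes onward, at most three scheduled readings remain (240, 300, 360).

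**Step 2: find the interval that would make the limbs agree.** With equal repeats d minutes apart, four readings span 3d. The values of d below are assumptions, because the protocol gives none.

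| d (min) | Span 3d (min) |
|---|---|
| 3 | 9 |
| 5 | 15 |
| 6 | 18 |
| 10 | 30 |
| 15 | 45 |

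Setting 3d = 15 gives d = 5. At exactly 5 minutes the span is 15, not more than 15, so the duration limb also needs to read 15 minutes or more.

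**Step 3: compare the Dose 2 wording.** A non-serious hypertension event after Dose 1 bars Dose 2 under Section 6.5 but not under the specific sentence in Section 7.1. A serious event bars it under both.

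**The case against.** The strongest reply is that the rule is a duration rule, and the count only shows how staff confirm it, using rapid repeats on the automated device. Repeats about 5 minutes apart would make the limbs nearly agree, and reading the count as four scheduled readings defeats the 15 minutes beside it. That is probably the intent. Section 4.1 also refers to a Psychotherapy Manual for further dosing-session detail; it was not supplied and may give an interval. What stands against this is that the protocol, which carries the rule twice, states neither the repeats nor their spacing.

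A reader might go further in four ways that the documents do not support.

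- **Transfers would be delayed by 90 to 180 minutes.** Those figures are spans of scheduled readings. Nothing forbids unscheduled ones, and staff who take them can apply the duration limb.
- **Participants would be unprotected.** Two therapists are in the room, a physician is close by during the early hours, and discharge needs a physician's judgment. Section 5.2 excludes uncontrolled hypertension in the past year and antihypertensive medication. None of these sets a repeat interval, but they limit the risk. Section 2.3 describes mean pressure as "peaking 30 to 60 minutes following psilocybin administration and returning to baseline levels after 90 to 180 minutes", but for doses above 0.3 mg/kg. The 15 mg dose falls below that for anyone over 15/0.3 = 50 kg, and the 25 mg dose for anyone over 25/0.3 = 83 kg, so that time course cannot simply be carried over to every session.
- **The 5-minute rest fixes the repeat interval.** It is a condition for taking a reading. Recumbent participants can be at rest continuously, so it sets no minimum gap between repeats.
- **Sections 6.5 and 7.1 contradict each other.** Following 6.5 satisfies both. Both sections also withhold Dose 2 for any sign of undue risk, and Section 5.5 pauses dosing after a Grade 3 or 4 event at least possibly related to the drug.

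**Conclusion.** The concern holds as a conflict within the written rule. On the protocol's own schedule, four consecutive readings take 90 to 180 minutes against a stated 15, and a first high value at 240 minutes or later can never meet the count. The two limbs line up only under a 5-minute repeat interval that the protocol does not contain.

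It is a minor safety-rule correction. No endpoint or planned analysis changes. There are 10 × 2 = 20 planned dosing sessions, and the documents do not allow an estimate of how many would include a value over the limit. The conclusion rests on the protocol text alone; an interval in a manual that was not supplied would reduce the practical effect but would leave the protocol's stated equivalence unexplained.

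The difference between Sections 6.5 and 7.1 is a separate and smaller matter of inconsistent wording.

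**What to change.** In Sections 8.1.1 and 8.5, state that any reading above 200 systolic or 110 diastolic, including the one at 360 minutes, triggers automated repeats every 5 minutes, or at another short interval set by the study physician, with the participant kept at rest. Transfer if pressure is still over the limit at 15 minutes or more. At 5-minute spacing that is the initial reading plus three repeats. If another interval is chosen, restate the count to match it.

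The cost is a wording change in two sections and up to three extra cuff readings per high value, which interrupt the session. The automated device is already specified.

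Separately, use one event class in Sections 6.5 and 7.1. The clinical team should choose it, because the choice has consequences. The stricter 6.5 wording would withhold Dose 2 after non-serious hypertension, and Table 7 admits only participants with two doses to the Full Analysis Set, so each such participant would leave the efficacy analysis of a study planned for about 10. The 7.1 wording keeps them eligible unless the undue-risk clause applies.
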